#### **5.2.1.4. Data Review by Cardiac Core Lab** (refer to Operations Plan/ Imaging Charter)

##### **19. Part A** (To address Objective 2a): Analysis of paired sets of strips.

- a) The Sponsor will prepare one paired set of strips from approximately 140 randomly selected subjects (70 AF, 70 SR) (approximate strips = 280 strips)
  - i. One set includes a Lead 1 strip from the 12-lead and a paired strip from the SUT.
  - ii. The first reading from data collection will be used for all subjects.
- b) Cardiac Core Lab review:
  - i. Three blinded, independent cardiac technicians will review each paired set of strips. The strips will be rendered semi-transparent through the use of back lighting and overlaid to visually assess for morphological similarity.
  - ii. One reviewer will identify the first six consecutive distinct readable PQRST complexes without artifact that match between the strips for evaluation. For example, if the reference strip has an artifact in beats 2 and 5 but all other beats are good and the strip from the SUT has artifact in beats 1 and 6 but all other beats are good, the six consecutive beats to be used will begin at beat 7 of both strips. The strip will be excluded if six consecutive beats cannot be found. The six PQRST complexes identified by the initial reviewer will be used by the 2 other reviewers.
  - iii. Each reviewer will assign a pass/fail to the strips by visually assessing all 6 PQRST complexes. A "pass" is given when the morphology of the PQRST complexes appears to overlay to the unaided eye.
  - iv. Measure R amplitude from the isoelectric baseline to the nearest millimeter for the first two QRS complexes in both the reference strip and SUT strip. The reviewers will be blinded to the identity of the reference strip and SUT strip. Record these lengths.

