#### 5.3.2. Secondary Objectives/Endpoints

Two hypotheses associated with secondary objective 2a to demonstrate that the SUT produces a waveform that provides clinically equivalent information to the gold standard Reference will also be tested.

The first hypothesis is aimed at demonstrating that the proportion of subjects with a pass rating based on the visual assessment of 6 consecutive readable PQRST complexes is at least 80%.

The majority result from the pass/fail readings of the three independent cardiac technicians will be used for analysis. The hypothesis for this objective can be stated as follows:

$$H_{03}: \Pi_1 = 0.80$$

vs.

$$H_{A3}: \Pi_1 > 0.80$$

where  $\Pi_1$  represents the true population subject success proportion of pass ratings.

The second hypothesis associated with objective 2a is based on the results of the quantitative analysis of the R-wave amplitudes as measured by each of three cardiac technicians on the paired SUT and Reference strips in Part A. The majority result from the three technicians (i.e., if at least two technicians measure the difference in amplitudes between the SUT and reference strip to be  $\leq 2$ mm, then the paired strips for a given subject will be deemed  $\leq 2$ mm) will be used for testing the hypothesis that the proportion of paired R-Wave amplitude measurements  $\leq 2$  mm of each other is at least 80%

$$H_{04}: \Pi_2 = 0.80$$

vs.

$H_{A4}: \Pi_2 > 0.80$

where  $\Pi_2$  represents the true population agreement proportion of paired R-Wave amplitude measurements. For each participant, the QRS complex from the 12-lead ECG with the largest R amplitude (out of the two QRS complexes with R-wave amplitude measurements will be used for purposes of determining the majority result.

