### 5.3.4 Randomization and Blinding

This study is not randomized. Cardiac technicians will be blinded in Part A and will not know which strip is the Reference vs SUT strip. U.S. board-certified cardiologists in Part B-1 and board-certified cardiologist in Part B-2 will be blinded to the subject's past medical history and algorithm classification.

Approximately 140 subjects (70 SR; 70 AF) will be randomly selected to address objective 2a in Part A using a systematic sampling approach. A number between 1 and 4 will be randomly selected for the AF cohort and then every 4th consecutively enrolled AF subject will be selected at random within each site. Likewise, a number between 1 and 4 will be randomly selected for the SR cohort and then every 4th consecutively enrolled SR subject will be selected at random within each site.

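### Part A masks which strip is the reference but not that the two strips are a pair, and the protocol does not separate the R-amplitude readings from the overlay, so H04 is open to anchoring of unknown size

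*Combined protocol and SAP*

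**What the plan says.** Section 5.2.1.4, item 19b, makes the pair the unit of review: "Three blinded, independent cardiac technicians will review each paired set of strips". Item (i) adds "The strips will be rendered semi-transparent through the use of back lighting and overlaid to visually assess for morphological similarity". In item (ii) one reviewer picks six matching beats, which the other two then use. Item (iii) is the overlay score: "Each reviewer will assign a pass/fail to the strips by visually assessing all 6 PQRST complexes". Item (iv) is the measurement: "Measure R amplitude from the isoelectric baseline to the nearest millimeter for the first two QRS complexes in both the reference strip and SUT strip".

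For item (iv) the masking reads "The reviewers will be blinded to the identity of the reference strip and SUT strip". Section 5.3.4 says the same ("Cardiac technicians will be blinded in Part A and will not know which strip is the Reference vs SUT strip"), as does Section 3.4. All three places mask identity only.

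Section 5.3.2 bases H04 on "R-wave amplitudes as measured by each of three cardiac technicians on the paired SUT and Reference strips in Part A". A pair counts as agreeing "if at least two technicians measure the difference in amplitudes between the SUT and reference strip to be" 2 mm or less. H04 tests whether more than 80% of pairs agree, at one-sided 0.05 (Section 5.3.5).

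**The concern.** A label blind guards against favouring one device over the other. H04 is not exposed to that in any important way: it scores the size of the difference between two readings, and swapping the labels leaves that size unchanged. What matters for H04 is knowing that the two strips show the same beats of the same subject. A technician who knows this, and who may already have seen the tracings overlay, can let the first reading influence the second.

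H04 is the quantitative one of the two tests behind secondary objective 2a. H03 is a visual overlay judgement in which pairing cannot be hidden, so the amplitude reading is where an independent check is possible. If the second reading is pulled towards the first, recorded agreement rises without any better agreement between device and reference, in a test that succeeds by showing agreement above 80%. The 2-of-3 majority averages out errors that differ between technicians, not a bias that all three share.

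**Working it through.** **1. What is masked, step by step**

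| Step (item 19b) | Who | Identity masked? | Pairing masked? |
|---|---|---|---|
| (ii) mark six matching beats | one reviewer | yes | no, must compare both strips |
| (iii) overlay pass/fail | all three | yes | no, cannot be |
| (iv) R amplitude, both strips | all three | yes | not stated, though it could be |

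The score for H04 is |A − B| ≤ 2 mm per technician, then 2 of 3. Since |A − B| = |B − A|, hiding the labels does not change it.

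**2. The plan's own figure**

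Section 5.3.3 gives 88 subjects for H03 (null 0.80, true rate 0.90, one-sided 0.05, power at least 80%). No separate size is given for H04, which has the same null, alpha and strips. By the exact binomial test, n=88 rejects at 77 or more passes:

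- P(X ≥ 77 | 88, 0.80) = 0.0464
- P(X ≥ 77 | 88, 0.90) = 0.833

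So 88 reproduces. If all of the roughly 140 selected subjects contribute, rejection needs 121 or more, and P(X ≥ 121 | 140, 0.80) = 0.0320.

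**3. Sensitivity of H04 to shrinkage**

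Assumptions not in the documents: the measured difference d is Normal with mean 0; true agreement is exactly 80%; anchoring multiplies d by (1 − a).

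- SD from P(|d| ≤ 2) = 0.80: SD = 2 / 1.2816 = 1.561 mm.
- Recorded agreement: p(a) = 2Φ(2 / (1.561(1 − a))) − 1.
- Example, a = 0.05: 2 / (1.561 × 0.95) = 1.349, so p = 0.823.
- False rejection: P(X ≥ 77 | 88, p) or P(X ≥ 121 | 140, p).

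| Shrinkage a | Recorded agreement | False rejection, n=88 | False rejection, n=140 |
|---|---|---|---|
| 0 | 80.0% | 4.6% | 3.2% |
| 2% | 80.9% | 7.0% | 5.6% |
| 5% | 82.3% | 12.3% | 11.7% |
| 10% | 84.6% | 27.6% | 31.7% |

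**4. Does rounding or the majority rule remove it?**

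A simulation added rounding to whole millimetres, the 2-of-3 rule and reader-error SDs of 0.25, 0.5 and 1.0 mm, with the SD of the true difference reset so that unanchored agreement is about 80%. A 10% pull of the second reading towards the first gave recorded agreement of 84.3% to 84.9%. False rejection was 26% to 31% at n=88 and 29% to 36% at n=140. This is close to the simple formula, so neither feature removes the effect.

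**The case against.** Several points on the other side stand.

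- **Order is inferred.** A reader might infer that every technician measures strips just seen overlaid. The numbering (i) to (iv) suggests it, but item 19b gives no timing, session or order.
- **A document is unseen.** Section 5.2.1.4 refers to an Operations Plan/Imaging Charter, and Section 7.7 says a charter describes the independent review process. Coding and reading order could be set there. The supportable statement is that the protocol does not separate the readings, not that they are unseparated.
- **Direction is not certain.** A technician who has just scored a visible mismatch as a fail might read a wider gap. In the same model, expansion of 5% or 10% gives recorded agreement of 78% or 76%, which works against the sponsor. A pull towards agreement is the more plausible direction when the strips are known to show the same beats, but that is a judgement.
- **Discretion is limited.** The measurement is a length on a printed strip at standard scale, to the nearest millimetre, on pre-identified beats. This makes large shrinkage harder to defend. It does not exclude small shrinkage, because the score turns on a recorded 2 mm versus 3 mm.

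What does not fall is the central point: identity masking does little for an absolute-difference score, and the protocol states no other masking for it.

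**Conclusion.** The protocol leaves H04 exposed to anchoring between the two amplitude readings. The exposure follows from the text; its size does not, and the direction is plausible rather than shown. The table shows only how sensitive the test is: with true agreement at the 80% boundary and Normal differences, shrinkage of 2% to 10% takes the false-rejection chance from 4.6% to between 7% and 28% at n=88, and from 3.2% to between 6% and 32% at n=140.

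A reader might go further and conclude that H04 will be biased upwards, or that its error rate is known to be inflated. The documents support neither conclusion.

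The point is confined to one of the two tests for secondary objective 2a. Sensitivity and specificity do not use these readings, and for H03 the overlay is itself the assessment. This is a worthwhile, inexpensive improvement rather than a flaw in the main result.

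**What to change.** In Section 5.2.1.4, item 19b, set the order explicitly:

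1. One reviewer marks the beats on each pair, as now.
2. Each technician then measures R amplitude before any overlay scoring, on single strips carrying coded identifiers, in a random order that keeps a subject's two strips apart.
3. The strips are re-paired by code for the overlay pass/fail.

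State in item 19b(iv) and Sections 3.4 and 5.3.4 that amplitude readings are masked to pairing as well as identity. The reviewer who marks the beats has already seen the pairs, so that reviewer should measure only after all pairs are marked, from re-coded and reshuffled strips, and the text should not claim full masking to pairing for that reviewer. If the Operations Plan/Imaging Charter already contains such a procedure, stating it in these sections is enough.

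The cost is protocol and charter wording, plus coding and shuffling of about 280 strips. Technicians, number of readings and sample size are unchanged. The downside is slightly more core-lab handling and possibly a slightly lower agreement figure.

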##### **20. Part B-1** (To address Objective 1): Analysis of reference strips.

- a) The first reading from 12-lead ECG data collection will be used for all subjects (total strips = ~560). In the event that the planned sample size for analysis is not obtained due to a higher than expected amount of data loss, the 2nd and 3rd reading from data collection may be used as described in the statistical analysis plan (SAP).

- b) Three U.S. board-certified cardiologists out of a pool of nine cardiologists will review each complete 12-lead ECG (reference strip) and provide a diagnosis of the rhythm. (i.e. each reference strip will be reviewed independently 3x)
- c) The diagnosis of the rhythm will fall into one of four categories:
  - i. Sinus rhythm (SR)
  - ii. AF
  - iii. Other specific diagnoses should be called out (examples include normal sinus with premature ventricular contraction [PVC] (if  $\geq 4$  beats in the strip), normal sinus with PACS, 2nd degree block, AF with a rate  $>150$  bpm, supraventricular tachycardia [SVT], etc.)
  - iv. Unreadable = a diagnosis cannot be made as the strip is not adequate for reading.

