  - a) The Sponsor will prepare one paired set of strips from approximately 140 randomly selected subjects (70 AF, 70 SR) (approximate strips = 280)
    - i. One set includes a Lead 1 strip from the 12-lead and a paired strip from the SUT.
    - ii. The first reading from data collection will be used for all subjects.
  - b) Cardiac Core Lab review:

- i. Three independent cardiac technicians will review each paired set of strips. The strips will be rendered semi-transparent through the use of back lighting and overlaid to visually assess for morphological similarity.
- ii. One reviewer will identify the first six consecutive distinct readable PQRST complexes without artifact that match between the strips for evaluation. For example, if the reference strip has an artifact in beats 2 and 5 but all other beats are good and the strip from the SUT has artifact in beats 1 and 6 but all other beats are good, the six consecutive beats to be used will begin at beat 7 of both strips. The strip will be excluded if six consecutive beats cannot be found. The six PQRST complexes identified by the initial reviewer will be used by the 2 other reviewers.
- iii. Each reviewer will assign a pass/fail to the strips by visually assessing all 6 PQRST complexes. A “pass” is given when the morphology of the PQRST complexes appears to overlay to the unaided eye.
- iv. Measure R amplitude from the isoelectric baseline to the nearest millimeter for the first two QRS complexes in both the reference strip and SUT strip (reviewers will be blinded to the identity of the reference strip and SUT strip). Record these lengths.

20. **Part B-1** (To address Objective 1): Analysis of reference strips.

- a) The first reading from 12-lead ECG data collection will be used for all subjects (total strips = ~560). In the event that the planned sample size for analysis is not obtained due to a higher than expected amount of data loss, the 2nd and 3rd reading from data collection may be used as described in the statistical analysis plan (SAP).
- b) A pool of 3 to 9 blinded independent U.S. board-certified cardiologists will review each complete 12-lead ECG (reference strip) and provide a diagnosis of the rhythm. (i.e. Each reference strip will be reviewed independently 3x)
- c) The diagnosis of the rhythm will fall into one of four categories
  - i. Sinus rhythm (SR)
  - ii. AF

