## **Statistical Analyses**

Details of planned statistical analyses are included in the body of the protocol (Section 5.3).

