#### **4.5. Subject Withdrawal and Replacement**

A consented, enrolled subject may withdraw from the study for any reason. Subjects who withdraw prior to participation or who fail to complete study participation will be replaced.

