### 5.3.3 Sample Size

Under the assumption that the true population sensitivity is 95%, 231 subjects who are diagnosed with AF based on the 12-lead ECG reference strip and where the device algorithm classification produces a result of AF or SR will provide at least 80% power to reject its null hypothesis,  $H_{01}$ , using a one-sided type I error of 0.025. Moreover, under the assumption that the true population specificity is 96.5%, 226 subjects who are diagnosed with SR based on the 12-lead ECG reference strip and where the device algorithm classification produces a result of AF or SR will provide at least 80% power to reject its null hypothesis,  $H_{02}$ , using a one-sided type I error of 0.025. To account for obtaining readable waveforms, a minimum of 260 subjects with a known diagnosis of AF and approximately 300 subjects with no known diagnosis of AF will be enrolled. The sample size for AF subjects may be increased if the unreadable/unclassifiable rate is higher than originally assumed up to a maximum of 400 enrolled AF subjects.

For the secondary objective hypothesis,  $H_{03}$ , under the assumption that the true population subject success rate is 90%, 88 subjects will provide at least 80% power to reject its null hypothesis using a one-sided type I error of 0.05. To account for obtaining readable waveforms, approximately 140 subjects (70 SR; 70 AF) will be randomly selected.

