### 5.3.6 Missing Data/Outliers

Rigorous efforts will be made to ensure all subjects are compliant with the protocol. However, some subjects may drop out prematurely or some planned measurements may not be readable or obtainable. The data analyses will be conducted on all readable/classifiable data. Outliers may be removed from the analyses after investigation by the sponsor and biostatistician; any removal of data points from the analyses will be documented in the CSR. No outliers will be removed from the analyses of the primary or secondary endpoints.

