### 5.3.9 ANALYSIS SETS

Based on the results of the 12-lead ECG at screening, a minimum of 260 subjects are targeted to be enrolled into an AF cohort and approximately 300 subjects are targeted to be enrolled into a SR cohort to address objective 1. Approximately 140 of these subjects (70 SR; 70 AF) will be randomly selected to address objective 2a in Part A. The following analysis sets are defined for this study.

All Enrolled Analysis Set: All subjects who sign informed consent and are enrolled into the study. This analysis set will be used to summarize subject and ECG measurement accountability, demographic and baseline characteristics, safety data, and the ease of use data.

Classifiable Analysis Set: All subjects who have readable/classifiable paired SUT and Reference strip from Parts C and B-1, respectively. This analysis set will be used for analyzing the primary endpoints of sensitivity and specificity.

Waveform Assessment Analysis Set: Randomly selected subjects in Part A with paired SUT and Reference strips. If 6 consecutive paired beats for analysis cannot be found in these strips, they will be excluded from further analysis. This analysis set will be used for assessing the quality of the clinical waveform associated with secondary objective 2a.

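### Does the missing rule for second and third readings leave the primary analysis set undefined?

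*Combined protocol and SAP*

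**What the plan says.** Four places bear on a first reading that gives no usable result.

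- **Section 5.2.1.4, item 20 (repeated in the Synopsis).** The first 12-lead reading is used for every subject. The fallback is conditional: "In the event that the planned sample size for analysis is not obtained due to a higher than expected amount of data loss", the 2nd and 3rd "reading from data collection may be used as described in the statistical analysis plan (SAP"). Item 22 then applies the algorithm to the SUT strips that match those read in Part B-1.
- **Section 5.3.3.** The planned numbers are 231 AF and 226 SR subjects with the relevant reference diagnosis "and where the device algorithm classification produces a result of AF or SR will provide at least 80% power". Planned enrolment is at least 260 AF and about 300 SR. The AF sample size "may be increased if the unreadable/unclassifiable rate is higher than originally assumed up to a maximum of 400 enrolled AF subjects".
- **Section 5.3.6.** "The data analyses will be conducted on all readable/classifiable data".
- **Section 5.3.9.** The Classifiable Analysis Set is defined as "All subjects who have readable/classifiable paired SUT and Reference strip from Parts C and B-1, respectively". It does not name the reading.

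The Synopsis, under Statistical Analyses, says: "Details of planned statistical analyses are included in the body of the protocol (Section 5.3"). Nothing in 5.3.1 to 5.3.9 mentions a second or third reading.

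**The concern.** Sensitivity and specificity are the primary endpoints, and the strip that is scored should be fixed before anyone sees results. On a first reading of the plan, the same lost strips seem able to produce three analysis sets: fewer subjects, the planned number with some later readings, or the planned number of first readings from a larger AF cohort. Both remedies are permissive, their triggers are close to the same event, and no order is given. The reference that should settle the matter points to text that is not in Section 5.3.

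Three details sharpen the worry.

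- Data loss is not defined. Because 231 and 226 count only subjects with an algorithm result of AF or SR, it could be taken to include algorithm non-results.
- Staff coach the subject between recordings (item 11), so later readings may differ from the first.
- Section 5.3.3 gives no enrolment increase for SR, which leaves item 20 as the visible remedy there.

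At stake is whether a reader can confirm that the analysed strips were chosen by rule.

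**Working it through.** **1. Reproduce the planned numbers.** Inputs from 5.3.3 and 5.3.5: sensitivity 0.90 under the null and 0.95 assumed true; specificity 0.92 and 0.965; one-sided 0.025. The plan names no test, so an exact binomial test is assumed. Reject when X ≥ c, where c is the smallest integer with P(X ≥ c | n, p0) ≤ 0.025. Power is P(X ≥ c | n, p1).

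- AF, n = 231: c = 217, attained level 0.0239, power 81.6%.
- SR, n = 226: c = 216, attained level 0.0246, power 82.8%.

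Each is the smallest n that reaches 80% power, so the stated figures reproduce.

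**2. Loss that can be absorbed before any remedy matters.**

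- AF: 1 − 231/260 = 29/260 = 11.2%.
- AF at the enrolment limit: 1 − 231/400 = 169/400 = 42.25%.
- SR: 1 − 226/300 = 74/300 = 24.7%.

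**3. What each route delivers beyond that point.** The loss rates are assumptions; the documents give none. Each shortfall is assumed to be filled by a usable later reading.

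| Cohort | Assumed loss | First readings left | Later readings to reach plan | Enrolment to reach plan on first readings |
|---|---|---|---|---|
| AF (260) | 15% | 221 | 10 of 231 (4.3%) | 231/0.85 → 272 |
| AF (260) | 20% | 208 | 23 of 231 (10.0%) | 231/0.80 → 289 |
| AF (260) | 30% | 182 | 49 of 231 (21.2%) | 231/0.70 = 330 |
| SR (300) | 30% | 210 | 16 of 226 (7.1%) | no increase stated |
| SR (300) | 35% | 195 | 31 of 226 (13.7%) | no increase stated |
| SR (300) | 40% | 180 | 46 of 226 (20.4%) | no increase stated |

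The AF enrolment figures all lie within 400.

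**4. Does power separate the routes?** Not reliably. Exact power is saw-toothed in n, and 231 and 226 sit on peaks.

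| Cohort | n | c | Power |
|---|---|---|---|
| AF | 231 | 217 | 81.6% |
| AF | 230 | 217 | 73.7% |
| AF | 221 | 208 | 78.1% |
| SR | 240 | 230 | 77.7% |
| SR | 226 | 216 | 82.8% |
| SR | 225 | 216 | 73.4% |
| SR | 210 | 201 | 79.7% |

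Losing one subject costs more power than losing ten AF or sixteen SR subjects, and 240 SR subjects, above plan, have less power than 210. A smooth decline in power with loss appears only if the values of n happen to be chosen that way.

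**5. Could substituted strips move the estimate much?** As an illustration, take the 20% AF case and suppose the 23 later readings perform at the null value of 0.90 while the 208 first readings perform at 0.95. The pooled sensitivity is (208 × 0.95 + 23 × 0.90)/231 = (197.6 + 20.7)/231 = 0.945. That is a shift of 0.5 points, and nothing in the documents says which way it would go.

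**6. Read the passages together.** Section 5.3.3 operates while subjects are being enrolled. Item 20 comes into play only when the analysable number is still short. Section 5.3.6 says what goes into the analysis and does not exclude a substituted reading. The sequence is therefore enrol, substitute if still short, then analyse what is readable and classifiable. The analysis set counts subjects, which points to one strip pair each. A first reading that is readable but misclassified is not lost, so item 20, read naturally, gives no licence to replace it.

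**The case for a change.** The strongest case for a change is that the plan anticipates excess loss twice, offers two discretionary remedies, and cites a rule that is absent from the place where the Synopsis says it should be. Because Part C follows Part B-1, choosing another reference strip also changes which algorithm output is scored. Part B-2 stays on the first reading, so substitution would separate its strips from those in B-1 and C.

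The cross-reference defect and the undefined term stand. The rest carries less weight.

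- Item 20 cites a SAP, and 5.3 reads like a summary: it names no test and no rule for combining the three reference reads. A separate document may hold the rule. Its absence here does not show that the choice was left open.
- Part B-2 does not feed the primary endpoints, and the Part B-1 readers are blinded to the algorithm classification.
- SR enrolment is approximate and uncapped. Under 4.5, subjects in either cohort who withdraw before participating or "fail to complete study participation will be replaced". The looser wording in 6.6 covers the narrower case of early device removal, where the data may still be usable. It is not about which reading is analysed.
- The proposed remedy has its own difficulty. If algorithm non-results count as data loss, substitutes cannot be chosen wholly without sight of algorithm output, because that output shows who needs one. Only the AF or SR label could be withheld.
- Putting the AF enrolment increase ahead of substitution is a preference that the documents do not require. It would mean 12 to 70 more AF subjects at 15% to 30% loss (272 − 260 and 330 − 260).

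**Conclusion.** No change to the plan follows. This is missing detail that an analyst would fill sensibly: keep the first reading wherever it is usable, otherwise take the next usable reading in order, one per subject, without sight of the AF or SR label. The report would then give the number of substitutions, with sensitivity and specificity on first readings alone beside the main result. Following the plan in sequence gives a coherent analysis set, and neither a wrong result nor a direction of bias has been shown.

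The gap has no effect unless loss exceeds 11.2% in AF at minimum enrolment (42.25% at the limit of 400) or 24.7% in SR. At an assumed 20% AF loss it concerns at most 23 of 231 strips. These figures rest on the plan's own sample sizes, on illustrative loss rates, and on later readings being usable when needed. The power comparison should carry no weight, because exact power at 231 and 226 sits on saw-tooth peaks. If the document is revised for other reasons, citing the source of the reading rule in 5.3 would be a useful tidy-up.
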